### **7.2.2. Setting**

The POC feasibility study will be conducted in multiple population-based healthcare databases in various European countries.

### **7.2.3. Databases/Data Sources**

The POC feasibility study will be conducted on data in electronic healthcare databases that reside with partners and associate partners of the ADVANCE consortium. Based on an assessment of the quality of information on exposure and outcomes, which will take place as part of the fingerprint process prior to study initiation for all the outcomes, the databases will be selected. The quality criteria for a database (i.e., inclusion criteria) are:

- a) Vaccination data on pertussis vaccine available
- b) At least one of the outcomes available; and
- c) Data access and clearance of protocol possible within timelines of the POC feasibility study.
- d) Comparison of the rate of events against country specific benchmarks

The list below provides an overview of potential databases, based on initial assessment of population sizes; this list will be updated with new associate partners in the consortium.

Based on the meta-data, fingerprint data, and discussions and information from the databases, parameters in table 5 will be collected and described. This will be the basis for a decision whether the databases will be eligible for the next step (estimation), eligibility may differ for the different POC protocols.

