**Table 4: Characteristics of the Databases of ADVANCE Partners**

Datasource Country_name	Coverage, Region	Type of data	Years covered	Size (N persons)	Outpatient diagnoses	Inpatient diagnoses	Vaccines general	Prescribed/ dispensed drugs
BE_network of sentinel GPs	National	Surveillance network (paper based)	Since 1979	Based on patient contacts	Some (surveillance of specific diseases)	Specific diseases	No	No
BE_Pedisurv	National	Pediatric surveillance network of specific rare disease	Since 2002	National case based	Specific diseases	Specific diseases	no	No
DK_SSI	National	Record linkage	1996 - 2014	7.5 million	Yes (ICD-10)	Yes (ICD-10)	yes	yes
DK-AUH	Regional (Aarhus)	Record linkage	2004 - 2013	1.7 million	Yes (ICD-10)	Yes (ICD-10)	partial	yes
ES_BIFAP	National	GP	2002 - 2013	4.8 million	Yes (ICPC+free text)	yes (as text)	No (only influenza)	yes
ES_FISABIO	Regional (Valencia)	Record linkage	Since 2005	5 million	Yes (ICD-9)	Yes (ICD)	yes	yes
ES_IDIAP	Regional (Cataluña)	GP	Since 2005	5.8 million	Yes (ICD-9)	Yes	yes	yes
FI_HPVCCHRT	Trial participants	HPV RCTs+ extension through record linkage	Prospective since 2007	Around 20,000	Yes (ICD-10)	Yes (ICD-10)	yes	yes
IT_ARS	Regional (Tuscany)	Record linkage			no	Yes (ICD-9)	Not yet	yes
IT_ASLCR	Regional (Cremona)	Record linkage	2002 - 2013	454,188	No	Yes (ICD9)	Yes	yes
IT_Arianna	Regional (Casserta)	GP + record linkage	Since 2000	1.1 million	ICD9	ICD9	Not yet	yes
IT_PEDIANET	Regional (Veneto)	Family pediatricians	2004 - 2014	77,021	Yes	Yes	yes	yes
NL_IPCI	National	GP linked to RIVM vaccine registries	1996 - 2014	1.8 million	Yes (ICPC)	Yes (from letters/specialist)	no	yes
NL_RIVM	National	Case surveillance of infectious disease	?	16 million base population	Some (surveillance of specific diseases)	Specific diseases	no	No
SE_KI	National	Record linkage	1998 - 2010	9.4 million	Yes (ICD-10)	Yes (ICD-10)	partial	yes
UK_RCGP	National	GP	2003 - 2014	2.0 million	Yes (READ)	Yes (READ)	yes	yes

---

---

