Vaccinations: BCG, DTaP, DTwP, polio, Hib, HPV, Seasonal Influenza	Granularity of vaccine exposure data 
 
vaccine type
 
ATC code
 
brand
 
	N	Percent of total (vaccinetype) for these levels	Vaccine fingerprint
	Recorded dose vs. Derived dose vs. sequence (all possible combinations)	Cross-tabulation		Vaccine fingerprint, R
	Vaccination records without dose	N		Vaccine fingerprint, R
	Coverage in birth cohorts at age ....	Estimated Coverage (per methodology as developed in ADVANCE)	Comparison against WHO data, VENICE and local information	Vaccine fingerprint, R
	Coverage by dose	histogram of doses		Vaccine fingerprint, R
Per database and event				
Events	Name of event			
	Availability of codes	List of available codes per data domain	Frequency of each code in input files	Event fingerprint, Jerboa
	List of components	Name and description of query		Event team
	Frequency of events as detected by each component algorithm	Table of frequency of possible combinations		Algorithm comparison module of Jerboa
	Frequency of event as detected according to chosen algorithm(s)	Frequency by year		Component analysis
	Chosen algorithm and reason			Component analysis
Validity	PPV of chosen algorithm(s)	%	confidence measure	Output of the validity workflow
	Sensitivity of chosen algorithm(s)	%	confidence measure	Output of the validity workflow
	Specificity of chosen algorithm(s)	%	confidence measure	Output of the validity workflow
	Procedure to obtain the above estimates			Output of the validity workflow
External benchmarks	Validation Studies	Summaries of previously conducted validation studies in the database		Event team & database experience
	Estimates of frequency of the event in the population	Available estimates with		Event team & database

	represented by the database according to external data sources (e.g. literature)	source (and comments)		experience
--	--	-----------------------	--	------------

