### 7.2.9. Limitations

In this POC feasibility study that tests and evaluates the ADVANCE system, tailored to generate rapid evidence on vaccine effects, there are several methodological limitations. These limitations will be assessed, and are an integral part of the system evaluation process. The following points are considered to be the expected limitations:

- Given that this POC feasibility study evaluates a system and its different processes, the epidemiological results produced (i.e. incidence rates and risk ratios) should not be considered as evidence that can be directly translated to inform epidemiological and pharmacovigilance decision-making processes. The epidemiological results produced in this POC feasibility study are part of a set of evaluation indicators to test the ADVANCE system and may not be the best or true estimates
- It could be possible that within the process of database selection it will become evident that proposed case definition(s) for the events are either different, or are differently interpreted, in a specific database or country. Different countries and databases could be using different case definitions. To address this limitation, the study will produce country-and database-specific analyses and results.
- Some event outcomes are signs and symptoms and not disease entities. The coding in databases might not be applicable to signs and symptoms (e.g. crying). Therefore, database extraction algorithms and strategies need to be adapted (e.g. include also free text search).
- Event codes in databases might contain the whole spectrum of potential, probable and confirmed cases. Given the POC feasibility study nature to test the system and to save costs and time, diagnostic codes will not be validated on a patient level using medical histories and charts.

- 
- It is expected that only a limited number of databases will have information on wP vaccination available. Therefore, the suggested strategies in the methods sections 7.4.3 (i.e. multiplying baseline incidence rates with IR ratios across databases, time periods, and wP/ aP data) will be applied. The additional use of literature information will be carefully evaluated and interpreted.
  - The type of database used (e.g. GP database, hospital database, claim database, etc) will influence incidence rates. To address this limitation, the study will produce country/ database-specific analyses and results.

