#### 7.3.1. Benefit/risk analysis

This POC study will yield incidence rates (during exposure window and after exposure window) plus relative risk estimates that will be used in the B/R analysis.

**Table 6: Evidence Required for Safety Outcomes to Build the Effects Table by Country, Year of Birth and for Each Outcome in the B/R analysis**

Incidence in risk period after wP or aP vaccination						
Time since dose**	Dose 1*		Dose 2		Dose 3	
	Inc	95% CI	Inc	95% CI	Inc	95% CI
Risk window 1						
Risk window 2						
Risk window 3						
Baseline incidence						
2-3 months						
3-4 months						
4-5 months						
...						

\* number of doses might depend on the country and year

\*\* risk windows might be different depending on the safety outcome

In addition, the relative risk estimate from the SCCS will be used as described in the analysis

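### Eligibility is set for a whole database on one recorded outcome, so a source that does not record mild reactions can still supply person-time, and near-zero absolute rates, for them

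*Protocol*

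**What the plan says.** **Admission.** Protocol Section 7.2.3 lists four criteria: pertussis vaccination data, "At least one of the outcomes available; and", feasible access and clearance, and "Comparison of the rate of events against country specific benchmarks". The quality assessment takes place "prior to study initiation for all the outcomes", and Table 5, which has a block headed "Per database and event", is the stated basis for the eligibility decision. Eligibility may vary between the pillar studies ("eligibility may differ for the different POC protocols"). Nothing makes it vary by outcome within this protocol, which has seven outcome groups.

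**Denominator.** Section 7.2.5 keeps every subject who meets the age and calendar criteria and has positive person-time. Section 7.2.8.3 uses that person-time as the denominator for each event's rate, stratified by database and country among other factors.

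**Empty strata.** Section 7.2.8.1 says that zero numerators produced by stratification lead to aggregation at a higher level.

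**Output.** Section 7.3.1 describes what the benefit-risk model needs: an "Effects Table by Country, Year of Birth and for Each Outcome". Database is not a dimension of that table.

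**Acknowledged limitation.** Section 7.2.9 states: "The type of database used (e.g. GP database, hospital database, claim database, etc) will influence incidence rates". Its remedy is country- and database-specific results.

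**The concern.** The outcomes present in different care settings. Convulsions often reach hospital, whereas somnolence, crying and injection-site reactions mostly do not. A database that sees only hospital diagnoses can pass the outcome criterion on convulsions alone and then supply child-time for all seven outcome groups. For the mild ones its numerator is close to zero because the events are not recorded, not because they did not occur.

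The study exists to deliver absolute baseline and risk-window rates to a benefit-risk model. A rate that is low through non-recording would enter that model as a low risk. Aggregating zero cells upward does not repair it. It moves the uninformative person-time into a larger denominator, and the reader can no longer see that the outcome was not captured.

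The problem also reaches imputed values. The Abstract says that databases without the wP period obtain their wP rate by multiplying their own baseline rate by an SCCS ratio from elsewhere. A baseline rate that is too low gives an imputed wP rate that is too low by the same factor.

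**Working it through.** The protocol gives no event count, sample size or power figure for this point, so there is nothing to reproduce. The check has three parts.

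**1. Is there a candidate that fits?** Table 4 gives:

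| Source | Persons | Outpatient diagnoses | Inpatient diagnoses | Vaccines |
|---|---|---|---|---|
| IT_ASLCR | 454,188 | No | Yes | Yes |
| IT_PEDIANET (family pediatricians) | 77,021 | Yes | Yes | Yes |

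Both are Italian, and the Abstract names Italy among the countries with eligible databases.

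**2. Size if the two were combined into one country rate.** Let *w* be IT_PEDIANET's share of the child person-time and *s* the capture in IT_ASLCR relative to IT_PEDIANET. Then

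country rate / IT_PEDIANET rate = *w* + (1 − *w*) × *s*.

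With *s* = 0 the understatement factor is 1/*w*. Head counts of children stand in for person-time. Table 4 does not give the number aged 0-6, so two sets of assumed shares are shown.

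*Assumption A: 5-10% of IT_ASLCR and 40-100% of IT_PEDIANET are aged 0-6.*
- IT_ASLCR children: 454,188 × 0.05 = 22,709; × 0.10 = 45,419.
- IT_PEDIANET children: 77,021 × 0.40 = 30,808; × 1.00 = 77,021.
- Mildest case: *w* = 77,021 / (77,021 + 22,709) = 0.77, factor 1.3.
- Worst case: *w* = 30,808 / (30,808 + 45,419) = 0.40, factor 2.5.

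*Assumption B: the rough share in Section 7.2.8.1 (5-8 of 34 million, 15-24%) applied to IT_ASLCR, and 50-100% of IT_PEDIANET counted.*
- IT_ASLCR children: 454,188 × 5/34 = 66,792; × 8/34 = 106,868.
- All of IT_PEDIANET: *w* = 77,021 / 143,813 = 0.536 and 77,021 / 183,889 = 0.419, factors 1.9 and 2.4.
- Half of IT_PEDIANET (38,510): *w* = 38,510 / 105,302 = 0.366 and 38,510 / 145,378 = 0.265, factors 2.7 and 3.8.

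*Partial capture.* With *s* = 0.25, the worst case under A becomes 0.40 + 0.60 × 0.25 = 0.55 (factor 1.8). Under B it becomes 0.265 + 0.735 × 0.25 = 0.449 (factor 2.2).

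If only databases that capture the outcome enter numerator and denominator, the ratio is 1 by construction.

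**3. Which quantities are affected?**
- *Database-stratified rates:* IT_PEDIANET's rate is untouched. IT_ASLCR's own rate is *s* times what a capturing source would show, so it is near zero when *s* is.
- *SCCS ratio:* if capture is the same in risk and baseline time, *s* appears in both and largely cancels.
- *Imputed wP rate (baseline × ratio):* *s* stays in the baseline rate and carries through in full.

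**The case against.** The case on the other side is substantial, and several stronger readings do not survive it.

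- **A reader might infer that the per-event assessment plays no part in inclusion.** It does. Section 7.2.3 makes Table 5 the basis for the decision, and the benchmark criterion compares event rates with country figures, which should expose a source with an implausibly low fever rate. What remains is that the decision is taken for the database as a whole. The benchmark criterion has no threshold and no stated consequence for a single outcome.
- **A reader might infer that dilution of country rates is certain.** No passage orders pooling of unlike sources. Sections 7.2.8.3 and 7.2.9 provide for database-level rates, and the Abstract applies the wP imputation within each database. The way databases become a country row may be settled in the benefit-risk protocol or the SAP, neither of which is shown, so silence on that step is not the defect. Database-level reporting prevents mixing in the study's own tables. It does not make a non-recording source's own rate valid, and it does not govern Table 6 or the aggregation of zeros.
- **A reader might take total head counts and report a 6.9-fold error** (531,209 / 77,021). Those are all-age counts for IT_ASLCR and are not child person-time, so the figure is not supported.
- **A reader might infer a spurious wP-aP difference.** The protocol gives no mix of sources by vaccine period, so this cannot be shown.
- **The example is a candidate.** Table 4 lists potential databases, not the final selection. IT_ASLCR also holds drug data, and Section 7.2.7.2 and Appendix 1 allow proxies such as drugs, so zero capture is an upper limit on the problem.

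Section 7.2.9 also discloses that database type affects rates and warns that the estimates may not be the true ones. Disclosure does not change the rules that would produce an invalid cell.

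**Conclusion.** The concern holds in limited form. The protocol collects the evidence needed to judge capture per database and outcome, but it applies eligibility to whole databases, keeps all person-time for every event and aggregates zeros upward. Followed as written, these stated rules can produce near-zero absolute rates that reflect missing records, and they can place such a source inside a country-level effects table.

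The size is conditional. For the one Italian pair that Table 4 illustrates, pooling with zero capture would understate mild-reaction rates about 1.3- to 2.5-fold under assumption A and 1.9- to 3.8-fold under assumption B. Every age share is an assumption, as are pooling and zero capture, and partial capture shrinks the effect. Absolute rates and baseline-times-ratio imputations are exposed; the SCCS ratio mostly is not. The point is worth correcting before estimation because the remedy uses data already being collected.

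**What to change.** 1. In Section 7.2.3, use the per-event block of Table 5 to set eligibility per database and outcome, and record the result in a database-by-outcome grid.
2. In Sections 7.2.5 and 7.2.8.3, count events and person-time for an outcome only in databases judged to capture it.
3. Report the remaining cells as 'not captured', not as zero, and exempt them from the zero-numerator aggregation rule in Section 7.2.8.1.
4. Add database as a dimension of Table 6, or state that a country row combines only databases eligible for that outcome.

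The cost is protocol wording and one grid filled from the fingerprinting output. The real downside is fewer databases, and so wider intervals, for the mild outcomes. Some countries may have no estimable rate for some of them.

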**Table 4: Characteristics of the Databases of ADVANCE Partners**

Datasource Country_name	Coverage, Region	Type of data	Years covered	Size (N persons)	Outpatient diagnoses	Inpatient diagnoses	Vaccines general	Prescribed/ dispensed drugs
BE_network of sentinel GPs	National	Surveillance network (paper based)	Since 1979	Based on patient contacts	Some (surveillance of specific diseases)	Specific diseases	No	No
BE_Pedisurv	National	Pediatric surveillance network of specific rare disease	Since 2002	National case based	Specific diseases	Specific diseases	no	No
DK_SSI	National	Record linkage	1996 - 2014	7.5 million	Yes (ICD-10)	Yes (ICD-10)	yes	yes
DK-AUH	Regional (Aarhus)	Record linkage	2004 - 2013	1.7 million	Yes (ICD-10)	Yes (ICD-10)	partial	yes
ES_BIFAP	National	GP	2002 - 2013	4.8 million	Yes (ICPC+free text)	yes (as text)	No (only influenza)	yes
ES_FISABIO	Regional (Valencia)	Record linkage	Since 2005	5 million	Yes (ICD-9)	Yes (ICD)	yes	yes
ES_IDIAP	Regional (Cataluña)	GP	Since 2005	5.8 million	Yes (ICD-9)	Yes	yes	yes
FI_HPVCCHRT	Trial participants	HPV RCTs+ extension through record linkage	Prospective since 2007	Around 20,000	Yes (ICD-10)	Yes (ICD-10)	yes	yes
IT_ARS	Regional (Tuscany)	Record linkage			no	Yes (ICD-9)	Not yet	yes
IT_ASLCR	Regional (Cremona)	Record linkage	2002 - 2013	454,188	No	Yes (ICD9)	Yes	yes
IT_Arianna	Regional (Casserta)	GP + record linkage	Since 2000	1.1 million	ICD9	ICD9	Not yet	yes
IT_PEDIANET	Regional (Veneto)	Family pediatricians	2004 - 2014	77,021	Yes	Yes	yes	yes
NL_IPCI	National	GP linked to RIVM vaccine registries	1996 - 2014	1.8 million	Yes (ICPC)	Yes (from letters/specialist)	no	yes
NL_RIVM	National	Case surveillance of infectious disease	?	16 million base population	Some (surveillance of specific diseases)	Specific diseases	no	No
SE_KI	National	Record linkage	1998 - 2010	9.4 million	Yes (ICD-10)	Yes (ICD-10)	partial	yes
UK_RCGP	National	GP	2003 - 2014	2.0 million	Yes (READ)	Yes (READ)	yes	yes

---

---

***UK\_THIN***

National

GP

1996-2013

8.3 million

Yes (READ)

Yes (READ)

yes

yes

---

**Table 5 Assessment sheet for the quality / feasibility of the database to participate in the POC studies**

Quality of information				
META-DATA				
Category	Data	Measure(s)		Origin of information
Provenance of information	Sources for diagnoses (as codes or text) 
 
• primary care
 
• outpatient specialist
 
• hospital discharge
 
• emergency admission
 
• causes of death
 
	per type yes/no	Certain missingness?	Data provenance questionnaire to databases
	Vaccinations 
 
• routine childhood
 
• HPV
 
• travel
 
• influenza
 
• voluntary
 
 Drugs 
 
• prescribed/dispensed primary by GP
 
• prescribed/dispensed by specialist
 
• prescribed/dispensed during hospitalization
 
	per type yes/no	Certain missingness?	AIRR survey
	Diagnostic tests 
 
• primary care
 
• outpatient specialist
 
• during hospitalization
 
	yes/no	Certain missingness? Results?	AIRR survey
POPULATION				
Size	Number of lives (at any point in time) in population	N		Population fingerprint
	Number of subjects active at 1/1/2015	N		Population fingerprint
Dates	Missing Birthdate (no valid date entry (to be supplied by database owner)	N	Percentage on total number of lives	Attrition diagrams DBs
	Birth dates (day of birth independent of month)	Frequency of each day of the month of the DOB (1-31)	Percentage on total number of lives	Vaccine fingerprint (R)
Observation Time & lag time	Origin for the start of follow-up 
 
• birth (start of follow-up = birth)
 
• registration with database (start of follow-up > 1 month after date of birth)
 
	N	Percentage of total	Jerboa Event fingerprint
	Origin for the end of follow-up 
 
• death (end of follow-up = date of death in event file)
 
• exiting from database (end of follow-up < last data availability for practice)
 
	N  Median (5 th , 95 th percentile of lag time from date of delivery till	Percentage of total	Jerboa Event fingerprint

		last data)		
Gender/age	Population age Distribution (Overall and by sex) * at 1/1/2015 (representativeness of population)	N	Compared to national statistics (see D5.2)	Population fingerprint
Per type of vaccination				
Vaccinations: BCG, DTaP, DTwP, polio, Hib, HPV, Seasonal Influenza	Granularity of vaccine exposure data 
 
vaccine type
 
ATC code
 
brand
 
	N	Percent of total (vaccinetype) for these levels	Vaccine fingerprint
	Recorded dose vs. Derived dose vs. sequence (all possible combinations)	Cross-tabulation		Vaccine fingerprint, R
	Vaccination records without dose	N		Vaccine fingerprint, R
	Coverage in birth cohorts at age ....	Estimated Coverage (per methodology as developed in ADVANCE)	Comparison against WHO data, VENICE and local information	Vaccine fingerprint, R
	Coverage by dose	histogram of doses		Vaccine fingerprint, R
Per database and event				
Events	Name of event			
	Availability of codes	List of available codes per data domain	Frequency of each code in input files	Event fingerprint, Jerboa
	List of components	Name and description of query		Event team
	Frequency of events as detected by each component algorithm	Table of frequency of possible combinations		Algorithm comparison module of Jerboa
	Frequency of event as detected according to chosen algorithm(s)	Frequency by year		Component analysis
	Chosen algorithm and reason			Component analysis
Validity	PPV of chosen algorithm(s)	%	confidence measure	Output of the validity workflow
	Sensitivity of chosen algorithm(s)	%	confidence measure	Output of the validity workflow
	Specificity of chosen algorithm(s)	%	confidence measure	Output of the validity workflow
	Procedure to obtain the above estimates			Output of the validity workflow
External benchmarks	Validation Studies	Summaries of previously conducted validation studies in the database		Event team & database experience
	Estimates of frequency of the event in the population	Available estimates with		Event team & database

	represented by the database according to external data sources (e.g. literature)	source (and comments)		experience
--	--	-----------------------	--	------------

#### **7.2.4. Source Population**

The source population in each of the eligible databases will be the pediatric population from birth to age six years or when receiving the booster dose at school entry that is registered in the participating databases.

#### **7.2.5. Population Selection**

The study population will comprise all children registered in any of the participating databases during the study period and for whom an adequate start and end of follow-up and date of birth can be defined. Children will be followed from start of the study period, one month after date of birth (i.e. to allow for pre-vaccination time for the SCCS design and to avoid pre-term related or birth-induced increase in incidence rates), or date of valid data in the database (whichever is the latest) until the end of study period (31-12-2015, the school-entry pertussis booster, transferring out of the database, death, reaching age 6 years: whichever is the earliest). Persons with missing dates of birth or sex will not be included.

For the incidence rate part of the study, we will retain all subjects meeting age and calendar time inclusion criteria with person time greater than zero.

The vaccination day and outcome-specific risk-windows after vaccination will be classified as risk periods, and the period between the end of the risk-window after vaccination until the next pertussis-containing vaccination or end of follow-up as the baseline period. To keep track of dose these periods will also be labeled by the number of previous pertussis-containing vaccinations. For all eligible subjects, CohortStart will be equal to PopulationStart and CohortEnd equal to PopulationEnd.

Databases will be asked to provide dates during which both wP and aP pertussis vaccines were both being used in the population. Patient time during the period of the switch from wP to aP will be removed from the cohort and SCCS analyses to avoid misclassification of exposures.

In order to avoid confounding by infections or other vaccinations, the study population for the incidence rate cohort design will NOT be the same as for the SCCS design.

For the self-controlled case series, analysis sets containing cases of each of the outcomes under study will be defined. For each of these cases, exposure will be defined as: exposed to wP and exposed to aP.

The study population for each outcome-specific SCCS analysis will be those subjects who experienced the event at least once during follow-up. Eligible person time for these subjects will be one month before the first recorded pertussis vaccine exposure until one month after the last pertussis vaccine exposure. Risk periods will be those specified for each outcome after each dose. Baseline periods will be days -31 to -8 before exposure and the interval from the last day of the risk window + 1 to day 31.

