#### SCCS

A pre-vaccine baseline risk period will be applied to control for the healthy-vaccinee effect. The SCCS will include age in days, and season (classified from the month) as time-varying covariates, as well as all available doses of pertussis vaccine as exposures. Conditional Poisson regression analyses will be conducted for the estimations.

10 describes the availability of wP information of two different databases (i.e. in database [Db] A, wP information is available and in Db B it is not) and the approach how IR within the risk period will be calculated.

**Figure 4: Approach How to Calculate Risk Window Specific IR in Databases where wP Information is Either Available or Lacking**

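### The SCCS ties observation and control time to the doses received, so its ratios are biased if a convulsion or HHE stops the series; size and direction depend on assumptions

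*Protocol*

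**What the plan says.** Protocol section 7.2.5 defines the SCCS cases as "those subjects who experienced the event at least once during follow-up". Their eligible time runs from "one month before the first recorded pertussis vaccine exposure until one month after the last pertussis vaccine exposure". On control time it says "Baseline periods will be days -31 to -8 before exposure", together with the days from the end of the risk window to day 31. For exposure it says "Risk periods will be those specified for each outcome after each dose".

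Section 7.2.8.3 (SCCS) puts age in days and season into the model, "as well as all available doses of pertussis vaccine as exposures", and states "Conditional Poisson regression analyses will be conducted for the estimations". The one safeguard named there is: "A pre-vaccine baseline risk period will be applied to control for the healthy-vaccinee effect". Days -7 to -1 are in neither the risk nor the control time.

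The limitations in section 7.2.9 do not mention events that change later vaccination. By contrast, the cohort part (section 7.2.7.1) follows children regardless of event or vaccination. The abstract and section 7.2.1 then carry the wP ratio into databases that hold no wP data.

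**The concern.** A standard SCCS needs two things: the event must not change later exposure, and it must not change when observation ends. Under section 7.2.5 both follow from the doses actually received.

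Suppose a child has a convulsion or HHE and gets no further pertussis dose. Observation then closes one month after the earlier dose, and the event can never count as a control-day event before a later dose. Those control days lose events, while the events that stopped the series are compared with a shorter window. Leaving out days -7 to -1 deals with a dose put off for a few days, not with one never given.

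At stake are the dose-specific ratios for the two outcomes where this is most plausible, and the wP ratio that is multiplied into other databases' baseline rates.

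**Working it through.** The protocol gives no ratio or sample size for the SCCS, so there is no figure to reproduce. The check asks what the planned likelihood converges to.

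**Inputs from the protocol.** Observation from 31 days before the first dose to 31 days after the last (one month read as 31 days, in line with the day limits given). Control days -31 to -8 and day 4 to day 31. Convulsion window 0-72 hours, taken as days 0-3, so 4 days.

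**Assumptions.** True ratio 3; flat baseline of 1 event per day (arbitrary units); three doses 30 days apart; one event per case. A control-day event stops all later doses with probability p, a risk-day event with probability q.

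**Days per case.**
- All three doses: 24 + 19 + 19 + 28 = 90 control days, plus 4 risk days per dose. The 19 are days 4-22, because day 23 is day -7 of the next dose.
- Stopped after dose 2: 24 + 19 + 28 = 71 control days.
- Stopped after dose 1: 24 + 28 = 52 control days.

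**Expected events.**
- All three doses: control 62(1-p) + 28; risk 12(1-q), 12(1-q), 12.
- Stopped after dose 2: control 26p; dose 2 risk 12q.
- Stopped after dose 1: control 26p; dose 1 risk 12q.

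An event before dose 1 that stops the series leaves no dose, so that child is not analysed.

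**Estimating equations.** Let N3, N2, N1 be the three group totals, with D3 = 90 + 4(ρ1+ρ2+ρ3), D2 = 71 + 4(ρ1+ρ2), D1 = 52 + 4ρ1:
- 12 = 4ρ3·N3/D3
- 12 = 4ρ2·(N3/D3 + N2/D2)
- 12 = 4ρ1·(N3/D3 + N2/D2 + N1/D1)

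**Numbers.**
- p = q = 0: N3 = 126, D3 = 126, all ratios 3.00. The bias comes only from event-dependent dosing.
- p = q = 0.5: N3 = 59 + 6 + 6 + 12 = 83, N2 = N1 = 13 + 6 = 19. The solution is 2.69/3.70/4.88. Check on dose 3: D3 = 90 + 4 × 11.27 = 135.08, and 83 × 19.52/135.08 = 11.99.
- p = 0, q = 0.5: N3 = 90 + 6 + 6 + 12 = 114, N2 = N1 = 6. The solution is 2.85/3.13/3.35. Check on dose 3: D3 = 90 + 4 × 9.33 = 127.32, and 114 × 13.40/127.32 = 12.00.

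| Stopping probability | Any event can stop the series | Only risk-window events stop it |
|---|---|---|
| 5% | 2.97/3.06/3.12 | not run |
| 10% | 2.93/3.12/3.25 | not run |
| 25% | 2.84/3.31/3.72 | 2.92/3.06/3.17 |
| 50% | 2.69/3.70/4.88 | 2.85/3.13/3.35 |

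**Other schedules, true ratio 3, 50%.**
- 2-4-6-18 months: 2.67/3.75/4.67/5.56 if any event stops the series; 2.72/2.98/3.13/3.24 if only risk-window events do.
- 2-3-4-11 months, any event: 2.40/3.21/4.14/5.27.

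**True ratio 1, 2-4-6-18 months, any event.** 10% gives 0.98/1.04/1.07/1.10; 50% gives 0.91/1.25/1.53/1.79.

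**One ratio pooled over doses, true ratio 3.** Any event at 50%: 3.5 to 3.9 depending on schedule. Risk-window events only at 50%: 3.00 (2-4-6 months) to 3.09 (30-day spacing).

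**Candidate remedies** (true ratio 1, any event, 50%, 2-4-6-18 months):
- Fixed observation end, otherwise as planned: 1.01/1.06/1.11/1.58.
- Joint analysis without pre-dose days, still ending after the last dose: 0.64/0.96/1.28/1.63.
- Each dose analysed alone, with control days after that dose to a fixed end: 1.00 throughout. This holds by construction under a flat baseline, since whether a dose was given does not depend on events after it.

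**The case against.** **Direction.** A reader might infer that ratios for dose 2 onwards are always inflated. The documents do not support that. They do not say that an event stops later doses, which events would, or how often. An event soon after vaccination is the more obvious trigger, and then the distortion is modest: on a 2-4-6-18 month schedule dose 2 is not inflated at all (2.98). If all eligible non-risk time counts as baseline rather than only the per-dose windows, later doses come out lower still. With every risk-window event stopping the series on that schedule, doses 1-4 are 2.30/2.72/2.98/3.19, against 2.47/2.95/3.27/3.51. This objection stands.

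**Export.** A reader might also infer that the wP ratio passed to other databases is materially wrong. The abstract speaks of one ratio, section 7.2.1 of ratios, so it is unclear whether export is by dose. If one pooled ratio is exported, the errors for dose 1 and later doses partly offset, fully so in some risk-window scenarios. Nor do the documents show that stopping differs between wP and aP. Both points stand.

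**Purpose.** Section 7.2.9 says that the results test a system and may not be the best estimates. That limits the consequence, but the ratios still feed the benefit-risk model. A separate analysis plan could add a sensitivity analysis; the observation rule, however, is fixed in the protocol itself.

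**Remedy.** Control days only after the dose give up the pre-vaccine period and are all at older ages than the risk days. This is a fair reason not to make that version the sole or primary analysis.

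**Conclusion.** The point holds in conditional form. The observation rule and pre-dose control days make the planned SCCS invalid whenever a convulsion or HHE leads to later doses not being given, and the protocol has no provision for this beyond a seven-day gap.

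The size is not known from the documents. Under the stated assumptions, at 10% stopping by any event the dose 3 ratio is about 8% too high (3.25/3 = 1.083). At 50% it is about 63% too high (4.88/3 = 1.627) and dose 1 about 10% too low (2.69/3 = 0.897). If only risk-window events stop the series, 50% gives about 12% too high at dose 3 (3.35/3 = 1.117) and a nearly unbiased pooled ratio. A rise across doses in the results could therefore be an artefact, but need not be. The calculation uses a flat baseline and treats doses as given on time or never; long deferral was not modelled. Nothing here bears on whether a dose should be given or withheld.

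**What to change.** In section 7.2.8.3, for convulsions and HHE, add a pre-specified analysis that is valid when the event affects later exposure. Two options are suitable:
- the SCCS extension for event-dependent exposures; or
- separate dose-by-dose comparisons of risk days with post-dose days, to a fixed end that does not depend on later doses, adjusted for age.

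Report it beside the section 7.2.5 analysis. If the two differ materially, say so wherever the wP ratio is applied to another database. Name event-dependent vaccination in section 7.2.9.

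Neither a fixed end of observation alone nor dropping pre-dose days within the joint model is sufficient, as the remedy figures show.

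The cost is some extra wording and programming, fewer control days and wider intervals. The post-dose-only option also relies on the age adjustment being right.
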